# **15. Record Retention and Reporting Responsibilities**

## **15.1. Responsibilities of the Investigator**

The investigator is responsible for the preparation, review, and signature (as applicable), and retention of the following records:

- All essential correspondence that pertains to the investigation
- Device use/disposition records
- Records of each subject's case history and exposure to the device. Case histories include the eCRFs and supporting data (source documentation), including, for example:
- Signed and dated consent forms
- Medical records, including, for example, progress notes of the physicians, the subject's hospital chart(s) and the nurses' notes
- All adverse event/device deficiency information
- A record of the exposure of each subject to the investigational device (e.g., date of implant procedure and follow-up assessment dates)
- Documentation of any deviation from the CIP, including the date and the rationale for such deviation
- Signed Investigator Agreement, signed and dated curriculum vitae of the PI, sub-investigator(s) and key members, signed Delegated Task List
- In Canada, Investigator's Agreement in accordance with Subsection 81(k) of the Medical Devices Regulations

*Medtronic Confidential*

- The approved CIP, Patient Information/Informed Consent Form, Investigator Brochure or Report of Prior Investigations, and any amendments
- Insurance certificate, where applicable
- IRB/EC Approval documentation and voting list
- Regulatory authority notification and approval documentation
- List of sponsor and monitoring contacts
- Training records
- Disclosure of conflict of interest of the PI and sub-investigator(s)

The investigator may withdraw from responsibility to maintain records by transferring custody to another person, who will accept responsibility for record and report maintenance. The Investigator is responsible for the preparation, review, signature, and submission of the reports listed in Table 5, Table 6, and Table 7 as applicable to the respective geography. These are also subject to inspection by government agencies and must be retained. Reports will be submitted to regulatory authorities per local reporting requirements/regulations.

**Table 5: Investigator records and reporting responsibilities applicable to the United States**

Report	Submit To	Description/Constraints
Withdrawal of IRB approval (either suspension or termination)	Sponsor	An investigator shall report to the sponsor, within 5 working days, a withdrawal of approval by the reviewing IRB of the investigator's part of an investigation. (21 CFR 812.150(a)(2)).
Progress report	Sponsor and IRB	The investigator must submit this report to the sponsor and IRB at regular intervals, but in no event less than yearly. (21 CFR 812.150 (3)).
Study deviations	Sponsor and IRB	Notice of deviations from the CIP to protect the life or physical well-being of a subject in an emergency shall be given as soon as possible, but no later than 5 working days after the emergency occurred. (21 CFR 812.150(a)(4))
Failure to obtain IC prior to investigational device use	Sponsor and IRBs	If an investigator uses a device without obtaining informed consent, the investigator shall report such use within 5 working days after device use. (21 CFR 812.150(a)(5))
Final investigator report	Sponsor, IRB s and Relevant Authorities	This report must be submitted within 3 months of study completion or termination of the investigation or the investigator's part of the investigation. (21 CFR 812.150(a)(6))
Other	IRB and FDA	An investigator shall, upon request by a reviewing IRB, FDA or any other regulatory agency, provide accurate, complete, and current information about any aspect of the investigation. (21 CFR 812.150(a)(7))

**Medtronic Confidential**

**Table 6: Investigator records and reporting responsibilities applicable to Canada**

Report	Submit To	Description/Constraints
Withdrawal of REB approval	Sponsor	The investigator must report a withdrawal of approval by the reviewing REB of the investigator's part of the investigation within 5 working days of the date of withdrawal. (Medtronic Requirement)
Study Deviations	Sponsor and REB as applicable	Any deviation from the clinical investigational plan shall be recorded together with the explanation of the deviation. Notice of deviations from the CIP to protect the life or physical well-being of a subject in an emergency shall be given as soon as possible, but no later than 5 working days after the emergency occurred. (Medtronic Requirement)
Final Report	REB, Relevant Authorities	This report must be submitted within 3 months of study completion or termination of the investigation or the investigator's part of the investigation. (Medtronic Requirement)
Adverse Device Effect Reporting (Mandatory Problem reporting)	Health Canada	DDs that have resulted in any of the consequences characteristic of an SAE on the patient, the user or any other person or could do so were it to reoccur must be reported to the Regulator within 72 hours after it comes to the attention of the qualified investigator.

**Table 7: Investigator records and reporting responsibilities applicable to Japan**

Report	Submit to	Description/Constraints
Co-investigator/Clinical Research Coordinators List	Head of Medical Institution	When the principal investigator assigns important parts of the clinical trial duties to co-investigators and/or clinical research coordinators, he or she shall prepare a list of the assigned duties and the individual performing the assigned duties, submit the list to the Head of Medical Institution on the list, and receive the understanding of such individuals. (MHLW Ordinance 36, 2005 Article 63)
Study Deviations	Sponsor and Head of Medical Institution	The investigator may implement a deviation from, or a change in, the protocol to eliminate an immediate hazard(s) to study subjects without prior IRB/EC approval. In this case, the investigator shall immediately submit to the sponsor, the Head of Medical Institution, and to the IRB/EC via the Head of Medical Institution, the description and reason for the deviation and the proposed revision to the protocol, if one is necessary, to receive agreement.

**Medtronic Confidential**

		All deviations, regardless of the reason, shall be submitted to the sponsor. (MHLW Ordinance 36, 2005 Article 66)
Summary of the Clinical Study Status	Head of Medical Institution	The principal investigator shall submit a summary of the clinical study status to the Head of Medical Institution in writing once a year, or more frequently if requested by the IRB/EC, to receive the continuation review by the IRB/EC. (MHLW Ordinance 36, 2005 Article 68)
Premature Termination or Suspension of the Clinical Investigation	Head of Medical Institution	When the principal investigator discontinues or suspends the clinical study, he or she shall promptly notify the Head of Medical Institution thereof in writing, and explain in detail in writing the discontinuation or suspension. (MHLW Ordinance 36, 2005 Article 69)
Completion of the Clinical Investigation	Head of Medical Institution	When the clinical study is completed, the principal investigator shall notify the Head of Medical Institution thereof in writing and report on a summary of the clinical study results in writing. (MHLW Ordinance 36, 2005 Article 69)

## 15.2. Responsibilities of the Sponsor

The Sponsor will maintain the following records, including but not limited to:

- All essential correspondence related to the clinical study
- Signed Investigator Agreement
- Signed and dated current curriculum vitae for each investigator
- Records of device shipment and disposition (shipping receipts, material destruct records, etc.)
- Adverse event and device deficiency information
- All data forms, prepared and signed by the investigators, and received source documentation and core lab reports
- CIP, investigator brochure or report of prior investigations and subsequent amendments
- Site monitoring reports
- Financial disclosure information
- Study training records for site participants and internal study staff members
- Contact lists of all participating investigators/investigative sites, study monitors and Sponsor staff members; Sponsor will maintain these lists and provide updates to the necessary parties
- Sample of device labeling attached to investigational device
- Insurance certificates
- Ethics Board approval documentation and voting list

***Medtronic Confidential***

- Regulatory authority notification and approval documentation
- Lab certificates /Lab normal ranges
- Statistical analyses
- Clinical study report

The Sponsor is responsible for the preparation of, the accuracy of the data contained in, the review of and the submission of the reports listed in Table 8, Table 9, and Table 10 as applicable to the respective geography.

**Table 8: Sponsor records and reporting responsibilities applicable to the United States**

Report	Submit To	Description/Constraints
Unanticipated Adverse Device Effect	Investigators, IRB, FDA, and relevant authorities	Notification within ten working days after the sponsor first receives notice of the effect. (21 CFR 812.150(b)(1))
Withdrawal of IRB approval	Investigators, IRB, FDA, and relevant authorities	Notification within five working days after receipt of the withdrawal of approval. (21 CFR 812.150(b)(2))
Withdrawal of FDA approval	Investigators, IRB, and relevant authorities	Notification within five working days after receipt of notice of the withdrawal of approval. (21 CFR 812.150(b)(3))
Investigator List	FDA	Submit at 6-month intervals, a current list of the names and addresses of all investigators participating in the investigation. (21 CFR 812.150(b)(4))
Progress Reports	IRB and FDA	Progress reports will be submitted at least annually. (21 CFR 812.150(b)(4)(5), 812.36(f))
Recall and device disposition	Investigators, IRB, relevant authorities and FDA	Notification within 30 working days after the request is made and will include the reasons for any request that an investigator return, repair, or otherwise dispose of any devices. (21 CFR 812.150(b)(6))
Failure to obtain IC	FDA	Investigator's report will be submitted to FDA within five working days of notification. (21 CFR 812.150(b)(8))
Final Report	Investigators, IRB, Regulatory authorities upon request, and FDA	Medtronic will notify FDA within 30 working days of the completion or termination of the investigation. A final report will be submitted to the FDA, investigators, and IRBs within six months after completion or termination of this study. (21 CFR 812.150(b)(7))

**Medtronic Confidential**

**Table 9: Sponsor records and reporting responsibilities applicable to the Canada**

Report	Submit To	Description/Constraints

Unanticipated Serious Adverse Device Effects (USADE)
	
REB, Investigators, Health Canada
	
Medtronic will notify investigators and Ethics Boards in all geographies as soon as possible, but not later than 10 working days after the sponsor first learns of the effect.
 
Preliminary and final reporting to the Canadian Ministry of Health of events occurring inside (always) or outside Canada (in case of corrective actions) that is related to a failure of the device or a deterioration in its effectiveness, or any inadequacy in its labeling or its directions for use and has led to the death or a serious deterioration in the state of health of a patient, user or other person or could do so were it to recur. Report a) within 10 days after awareness, if incident has led to death or a serious deterioration in the state of health of a patient, user or other person b) within 30 days, if incident has not led to death or a serious deterioration in the state of health of a patient, user or other person, but could do so were it to recur c) as soon as possible, if incident occurred outside of Canada and is related to a corrective action. (Canada Medical Device Regulations, SOR/98-282; Mandatory Problem Reporting 59(1), 59(2), 60 (1))

Serious Adverse Device Effects (SADE)
	
REB as applicable, Health Canada
	
Submit to Ethics Boards per local requirement. (ISO 14155)
 
Preliminary and final reporting to the Canadian Ministry of Health of events occurring inside (always) or outside Canada (in case of corrective actions) that is related to a failure of the device or a deterioration in its effectiveness, or any inadequacy in its labeling or its directions for use and has led to the death or a serious deterioration in the state of health of a patient, user or other person or could do so were it to recur. Report a) within 10 days after awareness, if incident has led to death or a serious deterioration in the state of health of a patient, user or other person b) within 30 days, if incident has not led to death or a serious deterioration in the state of health of a patient, user or other person, but could do so were it to recur c) as soon as possible, if incident occurred outside of Canada and is related to a corrective

**Medtronic Confidential**

		action. (Canada Medical Device Regulations, SOR/98-282; Mandatory Problem Reporting 59(1), 59(2), 60 (1))
Device Deficiency that might have led to an SADE	REB as applicable, Investigators, Health Canada	Submit to Ethics Board per local requirement. Submit to regulatory authority as per local requirement.
Premature termination or suspension of the clinical investigation	Investigators, REB, Health Canada	Provide prompt notification of termination or suspension and reason(s). (ISO 14155:2011)
Recall and device disposition	Investigators, REB, Health Canada	Notification within 30 working days of the request and will include the reasons for any request that an investigator return, repair, or otherwise dispose of any devices. (Medical Devices Regulation Mandatory Problem Reporting 63 – 65.1)
Final Report	Investigators, REB, and Health Canada if applicable	The investigator shall have the opportunity to review and comment on the final report. If a clinical investigator does not agree with the final report, his/her comments shall be communicated to the other investigator(s). The principal clinical investigator in each center shall sign the report. (ISO 14155:2011)
Study deviation	Investigators	Ensure that all deviations from the CIP are reviewed with the appropriate clinical investigator(s), are reported on the case report forms and the final report of the clinical investigation. Site specific study deviations will be submitted to investigators quarterly. (ISO 14155:2011)
Significant new information	Ethics Board and Health Canada	Ensure that the Ethics Boards and Regulatory Authorities are informed of significant new information about the clinical investigation. (ISO 14155:2011)

**Table 10: Sponsor records and reporting responsibilities applicable to Japan**

Report	Submit to	Description/Constraints
Premature termination or suspension of the clinical investigation	Head of Medical Institution Pharmaceuticals and Medical Devices Agency (PMDA)	When the sponsor suspends or discontinues the clinical trial, he or she shall promptly notify the heads of all the medical institutions and regulatory authorities thereof and the detailed reason therefor in writing. ( MHLW Ordinance 36, 2005 Article 32 )
Termination of development of investigational device	Head of Medical Institution PMDA	When the sponsor decides not to attach the documents concerning clinical trial records collected in the clinical trial to the authorization application, he or she shall promptly notify the

**Medtronic Confidential**

		heads of all the medical institutions other facilities engaged in the clinical trial thereof and the detailed reason therefor in writing. (MHLW Ordinance 36, 2005 Article 32)
Investigator List	Head of Medical Institution PMDA	
The sponsor shall beforehand submit the list of investigators to PMDA and Head of Medical Institution. (MHLW Ordinance 36, 2005 Article 10, Pharmaceutical and Medical Device Act Enforcement Regulations, Article 269, 275)
 
The sponsor shall submit the list of investigators to PMDA and Head of Medical Institution when making any changes in the list. (MHLW Ordinance 36, 2005 Article 51, Pharmaceutical and Medical Device Act Enforcement Regulations, Article 270, 275)

Important information concerning the quality, efficacy, and safety of the investigational device	Principal Investigator Head of Medical Institution PMDA	When new, important information is obtained, the sponsor shall revise the investigator's brochure. In addition, prior to revising the investigator's brochure, the sponsor shall report the information to the principal investigator, Head of Medical Institution, and regulatory authorities. (MHLW Ordinance 36, 2005 Article 28)
Clinical Trial Report	PMDA upon request	The sponsor shall prepare, according to the procedure, a clinical study report that summarizes the results, etc., of a clinical study when it is completed or discontinued. (MHLW Ordinance 36, Article 33)
Study deviation	Principal Investigator Head of Medical Institution as necessary	
Ensure that all deviations from the CIP are reviewed with the appropriate clinical investigator(s), are reported on the case report forms and the final report of the clinical investigation. (ISO 14155:2011)
 
When the monitor confirms deviation as a result of monitoring, the monitor shall notify the principal investigator and, as necessary, the Head of Medical Institution thereof. The monitor shall also request for appropriate measures to be taken to prevent such deviation in the future. (MHLW Ordinance 36, 2005 Article 30)

### 15.3. Record Retention

The investigator must retain the Investigator Site File, source documents, and the records listed in Section 15.1. Responsibilities of the Investigator, until informed by Medtronic they no longer need to be retained. At a minimum, the investigator must retain records for at least 3 years (or longer if required by local law) after the last approval of a marketing application and until there are no pending or contemplated marketing applications, or at least 3 years have elapsed since the formal discontinuation of the clinical study or clinical development of the investigational devices. The investigator should take measures to prevent accidental or early destruction of the study related materials.

Medtronic will maintain study records under its responsibility in accordance with federal laws and regulations, J-GCP and Medtronic policy.

## 17. Appendices

Appendix I: Informed Consent Template

Appendix II: Adverse Event Definitions

*Medtronic Confidential*

- Appendix III: Adverse Event Code List
- Appendix IV: Echocardiography Protocol
- Appendix V: Radiography Protocol
- Appendix VI: Cardiac Magnetic Resonance Imaging Protocol – Functional Parameters
- Appendix VII: Computed Tomographic Angiography (CT) Imaging Protocol
- Appendix VIII: Anatomic Measurements and Device Screening Guidelines
- Appendix IX: Explant Protocol
- Appendix X: Instructions for Use Document
- Appendix XI: SF-36 Questionnaire
- Appendix XII: Post-Implant CT Sub-Study

## 18. Version History

Version	Summary of Changes	Author(s)/Title
1.0	
Initial Release
 
Note: Version 1.0 of this document may not align to the version of the document determined in the Medtronic Trial Master File (RAD)
	
[Redacted]
 
[Redacted]
 
[Redacted]

2.0	
 
• Additional outcome measures added (technical success, device success)
 
• Modification of additional outcome measure (procedural success)
 
• Addition of implant maximum of 10 subjects per site
 
• Modification of event causality terms/definitions
 
• Minor administrative changes throughout
 
 
Note: Version 2.0 of this document may not align to the version of the document determined in the Medtronic Trial Master File (RAD)
	
[Redacted]
 
[Redacted]
 
[Redacted]

3.0	
 
• Addition of Canada as a planned geography
 
• Expanded scope of document to include Canadian regulatory requirements
 
• Clarified Primary Effectiveness Endpoint to include Echocardiography assessment should CMR not be available
 
• Minor administrative changes throughout
 
 
Note: Version 3.0 of this document may not align to the version of the document determined in the Medtronic Trial Master File (RAD)
	
[Redacted]
 
[Redacted]

**Medtronic Confidential**

4.0
	
 
• Addition of Japan geography
 
• Expanded scope of document to include Japan regulatory requirements
 
• Adjustment of pre-implant window for imaging requirements
 
• Addition of post-care lifelong Aspirin and prophylactic antibiotic therapy recommendation
 
• Addition of section regarding role & membership of screening committee
 
• Revised Appendix VII Anatomic Cardiac Magnetic Resonance Imaging Protocol to become a Sub-study including subsequent requirements
 
• Removed requirement for sites to perform anatomic measurements on CT and MRI images
 
• Minor administrative changes throughout
 
 
Note: Version 4.0 of this document may not align to the version of the document determined in the Medtronic Trial Master File (RAD)
	
[REDACTED]

5.0
	
 
• Added information describing additional size Harmony TPV device
 
• Addition of section describing a subset of subjects for initial implant of the Harmony TPV 25
 
• Addition of a post-implant CT sub-study Appendix XIII
 
• Adjustment of pre-implant window for imaging requirements
 
• Minor administrative changes throughout
 
	
[REDACTED]

6.0
	
 
• Added information describing additional modified TPV25 size Harmony TPV device
 
• Removed language allowing deferring subjects
 
• Added discharge CT and one month post-implant functional CMR for mTPV 25 implants
 
• Removed screening log requirements
 
• Updated Appendix XII for Post Implant CT Sub-study
 
• Minor administrative changes throughout
 
	
[REDACTED]

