## 5. Study Design

This is a prospective, non-randomized, multi-center study. Up to 40 subjects will be implanted at a total up to 15 centers in the United States, Canada, and Japan. It is anticipated that more than 40 subjects will be enrolled (i.e. consented) to meet the target of up to 40 implants as not all subjects will be anatomically suitable for implantation. No site shall implant more than 10 subjects in the pivotal cohort to avoid bias of the study results. Subjects who discontinue participation prematurely following implant will be included in the analysis of results (as appropriate) and will not be replaced in the enrollment of total study subjects implanted. All implanted subjects will receive the Harmony TPV. Each implanted subject will be followed for five years or until the subject's Harmony TPV is explanted.

The addition of the second device size (Harmony TPV 25) is intended to expand the number of patients anatomically suitable for implantation and will include a Roll-In cohort of Harmony TPV 25 subjects. The Roll-In phase is described in **Section 8.4. Harmony TPV 25 Roll-In Phase**. The addition of the larger sized valve completed the pivotal cohort of 40.

Following the completion of the 40 pivotal cohort of the TPV 22 and TPV 25, the TPV 25 was modified and is referred to as modified TPV 25 (mTPV 25). There will be an added cohort of up to 15 subjects implanted with the mTPV 25. This additional cohort will include 10 US implants and up to 5 OUS implants from Canada and/or Japan. The mTPV 25 cohort is described in **Section 8.5. Addition of mTPV 25 Cohort**. The study methods include the following measures to minimize potential sources of bias:

- A Screening Committee comprised of a subset of study investigators will confirm subject eligibility and anatomic suitability
- An external, independent Clinical Events Committee (CEC) will review and adjudicate, at minimum, all deaths and endpoint related adverse events. Safety endpoint results will be based on CEC adjudications.
- All sites will follow a standardized protocol for acquisition of echocardiographic endpoint data.
- An Echo Core Lab will evaluate all echocardiograms.
- A CMR Core Lab will evaluate all functional CMR results.
- Study endpoints, when appropriate, will be based on CEC or Core Lab assessments.
- Study sites will follow their institutional procedures for maintenance of echocardiography and imaging equipment used for assessing the study variables.

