## 1. Version History

Version	Summary of Changes	Author(s)/Title
1.0	Initial Release     Note: Version 1.0 of this document is     equivalent to Version 2.0 in the Medtronic     Trial Master File (RAD)	Principal Statistician
2.0	
 
Addition of Canada as a planned geography
 
Clarified Primary Effectiveness Endpoint to include Echocardiography assessment should CMR not be available
 
Addition of the definition of analysis cohort for outcome measure #7.
 
Minor administrative changes to match the Clinical Investigative Plan Version 3.0.
 
Note: Version 2.0 of this document may not align to the version of the document determined in the Medtronic Trial Master File (RAD)
 
	Principal Statistician
3.0	
 
Converted to the new version of template
 
Addition of Japan as a planned geography
 
Addition of TPV 25 and modified TPV 25 devices
 
Inclusion of Roll-In cohort in the 40-subject primary cohort
 
Clarified rescreened patients
 
Updated the analysis cohort for all device-related adverse events
 
Clarified analysis data for endpoints
 
Clarified analysis method for the primary efficacy endpoint
 
Inclusion of Native study cohort in the Harmony PMA submission
 
	Senior Statistician
4.0	Removed mixed effects model analysis for outcome measure #6: characterization of right ventricle remodeling	Senior Statistician

Revision 5.1

Page 5 of 24

[figure not shown]
Version Summary of Changes		Author(s)/Title
5.0	
 
Clarified the reason why the primary efficacy endpoint analysis for PMA excluded the mTPV 25 cohort.
 
Clarified core lab echo after the 6-month time window opening will be used for primary efficacy endpoint when 6-month echo occurred prior to 6-month window opening or missed
 
	Senior Statistician
5.1	
 
Administrative issue update for section 7.9.2.3
 
Administrative issue update for revision number in header and page 1, changed from 3.0 to 5.1.
 
	Senior Statistician

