#### 3. Introduction

This document outlines the detailed statistical methods to be implemented for the data collected within the scope of the Medtronic Coronary and Structural Heart (CSH) Harmony Transcatheter Pulmonary Valve (TPV) in patients who have congenital heart disease and are clinically indicated for pulmonary valve replacement. The purpose of this plan is to provide a framework which answers the study objectives in a statistically rigorous fashion, without bias or analytical deficiencies.

Specifically, this Statistical Analysis Plan (SAP) has the following purpose: to prospectively (a priori) outline the types of analyses and presentations of data that will form the basis for conclusions to be reached that will answer the study objectives outlined in the protocol, and to explain in detail how the data will be handled and analyzed, adhering to commonly accepted standards and practices of statistical analysis in the medical device industry.

The primary analysis for safety and effectiveness will be performed when the first 40 implanted subjects (including Roll-in TPV 25 subjects) have completed their 6-month follow-up. While the primary safety endpoint is measured at 30 days, primary objective analysis will be completed upon completion of the primary efficacy endpoint, which is measured at 6 months. Following the completion of the 40 pivotal cohort of the TPV 22 and TPV 25, the TPV 25 was modified and is referred to as modified TPV 25 (mTPV 25). A supplemental analysis will be performed when the 10 US implants of modified TPV 25 (mTPV 25) cohort have completed their 1-month follow-up for both safety and efficacy. Both cohorts will be pooled for additional analysis out to 5 years after the previously mentioned analyses are completed. Hence the primary efficacy endpoint analysis for PMA will not include the mTPV 25 cohort due to those subjects not being eligible for their 6-month visit at the time of PMA snapshot. Once all subjects from both cohorts finish their 6-month visit, the endpoint analysis will be repeated on all subjects.

The analysis population for the Harmony PMA will include subjects from the Harmony Pivotal Study in combination with the data from the Native Outflow Tract Transcatheter Pulmonary Valve Research Clinical Study (IDE #G120175). Note the Native study only includes TPV22 implants.

Revision 5.1 Page 8 of 24

Form Medtronic

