## 7.14 Changes to Planned Analysis

No procedure- or device- related reintervention was added as one component of being success for the primary efficacy endpoint, acceptable hemodynamic function at 6 months. This criterion is not explicit in the CIP; however, it was intended to be defined in the protocol.

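### The rule letting a later echo decide the 6-month primary efficacy endpoint was written after the last pivotal implant, is not listed as a change, and is not covered by any sensitivity analysis

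*Protocol*

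**What the plan says.** **Timing.** Protocol section 18 records for version 6.0: "Added information describing additional modified TPV25 size Harmony TPV device". Protocol section 5 places that device in time: "Following the completion of the 40 pivotal cohort of the TPV 22 and TPV 25, the TPV 25 was modified". The same section shows that completion refers to filling the cohort: "The addition of the larger sized valve completed the pivotal cohort of 40". In the SAP version history, the entry for 3.0 includes "Addition of TPV 25 and modified TPV 25 devices" and, in the same list, "Clarified analysis method for the primary efficacy endpoint". The entry for 5.0 includes "Clarified core lab echo after the 6-month time window opening will be used for primary efficacy endpoint", and limits this to a 6-month echo that was early or missed.

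**The rule.** SAP 7.9.2.2 takes the first echo after the 6-month window opens, either unscheduled or from the 1-year visit. Protocol 8.1 sets the 6-month window at 23 to 29 weeks and the 1-year window at 44 to 60 weeks. Protocol 4.2.2 and 12.2.2 define the endpoint at 6 months and contain no such rule.

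**Disclosure and testing.** SAP section 3 gives the plan's purpose as "to prospectively (a priori) outline the types of analyses and presentations of data". SAP 7.14 lists one departure for this endpoint: "No procedure- or device- related reintervention was added as one component of being success for the primary efficacy endpoint". SAP 7.9.2.3 plans worst-case, best-case and last-value analyses for cases that could not be assessed.

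**Decision.** Protocol 12.2.2 and SAP 7.9.2.2 declare the objective met if the point estimate is at least 75%. A Clopper-Pearson interval is reported but plays no part in the decision.

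**The concern.** A rule that settles which echo scores a subject helps determine the primary result. In a single-arm study with no masking described, a rule written once implanting is over may be written when some outcomes can already be known. That does not make the rule wrong. It does mean that the prospective label cannot simply be extended to it, and that a reader needs to see whether the conclusion depends on it.

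The plan as written does not allow that check. A substituted subject has a result, so on a plain reading of SAP 7.9.2.2 the subject is assessable and falls outside all three sensitivity analyses. No planned table shows the rate without substitution or the number of subjects substituted. At stake is whether a declaration of met or not met rests on 6-month data or on an echo taken as late as week 60, which is 31 weeks after the 6-month window closes (60 − 29 = 31).

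**Working it through.** **Step 1: order of events.** The version histories are used only for timing, not as a conflict with current text.

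1. The 40 pivotal implants of TPV 22 and TPV 25 are completed (protocol section 5).
2. The TPV 25 is then modified, giving the mTPV 25 (protocol sections 5 and 8.5; SAP section 3).
3. SAP 3.0 is the first SAP version to list the mTPV 25, so SAP 3.0 follows step 2.
4. SAP 5.0 follows SAP 3.0 and records the later-echo rule.

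The rule therefore follows the 40th pivotal implant. No calendar dates are needed. If completion meant completed follow-up rather than completed implants, the rule would be later still.

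**Step 2: what can and cannot be placed after the 40th implant.**

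| Item | Where recorded | Timing |
|---|---|---|
| Later-echo rule | SAP history, 5.0 | After the 40th implant |
| Clarified efficacy analysis method | SAP history, 3.0 | After the 40th implant, but content not stated |
| Reintervention component | SAP 7.9.2 and 7.14 | Version of entry not stated |
| Scoring tables | SAP 7.9.2.2 | Version of entry not stated |

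**Step 3: leverage of one substituted echo.** Let X be successes and n evaluable subjects, with n at most 40. Met means X/n ≥ 0.75. In the tables of SAP 7.9.2.2, a missing 6-month echo is generally not evaluable, and SAP 7.9.2.3 excludes such subjects from the primary rate. Substitution therefore moves a subject from excluded to counted.

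- Substituted success: 29/39 = 74.4%, not met, becomes (29 + 1)/(39 + 1) = 30/40 = 75.0%, met.
- Substituted failure: 29/38 = 76.3%, met, becomes 29/(38 + 1) = 29/39 = 74.4%, not met.
- If an early echo would otherwise have been used, replacing it changes only the numerator: 30/40 = 75.0% against 29/40 = 72.5%, in either direction.

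**Step 4: how close the total must be.** Suppose the final count is X of 40 and m of those successes came from substituted echoes. Without them the rate is (X − m)/(40 − m), which reaches 0.75 only if X ≥ 30 + m/4.

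- With m from 1 to 4, the conclusion depends on the rule only when X is exactly 30.
- With m = 5 it can also depend on it at X = 31: 31/40 = 77.5%, met, against 26/35 = 74.3%, not met.

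If the true success rate were 75%, 80% or 85% (assumed; the documents give no expected rate), the binomial chance that X = 30 of 40 is 14.4%, 10.7% or 3.7%. These bound the chance that a single substituted success is decisive when all 40 are evaluable.

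**The case against.** The strongest reply has four parts.

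- **The rule fills a gap.** Protocol 12.2.2 says nothing about early or missed echoes, so a rule was needed, and supplying one is arguably not a change to the planned analysis. The need stands. But SAP 7.14 already lists the reintervention criterion on the footing that the protocol left it unstated although it was intended. By that standard the later-echo rule belongs there too.
- **The history calls it a clarification.** SAP 1.0 to 4.0 are not available, so an earlier form of the rule cannot be excluded. This stands as a limit. If earlier text existed, 7.14 can say so.
- **The sequence is disclosed and the objective is descriptive.** There is no hypothesis test, the echoes are read by a core laboratory, and SAP section 3 expects additional analyses. All true. Even so, a met or not-met statement is made against 75%, and no planned analysis isolates the rule.
- **The rule is not shown to favour the sponsor.** This stands: a substituted echo can be a success or a failure.

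A reader might go further and infer that all the added scoring rules came late, that outcomes had been seen, or that most subjects had already passed the 6-month window. The documents support none of these. The reintervention component has no stated entry date, is openly listed, and can only lower the success rate. No passage says whether results had been reviewed when SAP 5.0 was written. Protocol 5.1 only estimates an enrolment period, and enrolment there means consent, not implant. The larger valve was also introduced in stages, so no share of subjects past the window can be derived.

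**Conclusion.** The point holds for the later-echo rule. It was written after the pivotal cohort had been fully implanted, it is missing from the protocol definition and from SAP 7.14, and the planned sensitivity analyses do not test it. The prospective description in SAP section 3 therefore needs qualifying for this rule. The same caution applies to the efficacy method clarified in SAP 3.0, to the extent that it changed scoring, which the documents do not show.

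The effect could be nil. If no subject was scored on a substituted echo, nothing changes. If one or more were, the conclusion turns on the rule only when the result lies close to 75%. The conclusion assumes that the versions were issued in numerical order and that completing the cohort means at least completing its implants. It is a finding about timing and transparency. It does not say that the rule is unreasonable or was chosen with the results in view.

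**What to change.** 1. **SAP 7.9.2.3.** Add the primary efficacy rate from 6-month in-window data only (weeks 23 to 29), without later-echo substitution and with the reintervention component kept. An unscheduled echo taken inside the window is in-window data and can stay. In the worst-case and best-case analyses, treat the substituted subjects as unassessable. Report how many subjects were scored on a substituted echo, and their results.
2. **SAP 7.14 and section 3.** List the later-echo rule and any other primary-efficacy scoring rule first written in SAP 3.0 or later. For each, state when it was written and what outcome data were accessible at the time. Limit the prospective statement in section 3 accordingly.
3. **Reporting.** If the primary and in-window rates fall on opposite sides of 75%, say that the conclusion depends on the later-echo rule. Requiring both rates to reach 75% is not proposed, since that would itself be a new success criterion set after enrolment.

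The cost is one extra table row from data already held, a few lines of SAP text, and possibly a less favourable statement if the two rates straddle 75%.
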